## 9.10. Early Discontinuation/Withdrawal of Participants

During the course of the trial a participant may choose to withdraw early from the study at any time, without giving reasons, and without prejudicing their clinical care.

Participants will not have the option to withdraw the data collected up until the point of withdrawal, as the data will be required for the intention-to-treat (ITT) main analysis and analysis of safety. The options for withdrawal will be explained clearly in the PIS. The type of withdrawal and reason for withdrawal, if the participant is willing to provide one, will be recorded in the withdrawal CRF.

In addition, the Investigator may discontinue a participant from the study treatment at any time if the Investigator considers it necessary to safeguard the safety or wellbeing of the participant, including but not limited to ineligibility (either arising during the study or retrospectively having been overlooked at screening).

Withdrawn participants will not be replaced.

## 9.11. **Definition of End of Study**

The end of the study is defined as the last follow up of the last participant and once all queries have been resolved.

## **10. SAFETY REPORTING**

Safety reporting for each participant will begin from randomisation and will end when the participant has reached their final main follow-up time point, at 6 months post-randomisation.

## 10.1. **Definition of Serious Adverse Events**

Clinical Research Protocol Template version 15.0

CONFIDENTIAL

© Copyright: The University of Oxford and Oxford University Hospitals NHS Foundation Trust 2019 Page 23 of 39

A serious adverse event is any untoward medical occurrence that:

- results in death
- is life-threatening
- requires inpatient hospitalisation or prolongation of existing hospitalisation
- results in persistent or significant disability/incapacity
- consists of a congenital anomaly or birth defect

Other 'important medical events' may also be considered a serious adverse event when, based upon appropriate medical judgement, the event may jeopardise the participant and may require medical or surgical intervention to prevent one of the outcomes listed above.

NOTE: The term "life-threatening" in the definition of "serious" refers to an event in which the participant was at risk of death at the time of the event; it does not refer to an event which hypothetically might have caused death if it were more severe.

# 10.2. **Reporting Procedures for Serious Adverse Events**

If an SAE arises in the period between randomisation and the final follow-up visit, that is deemed related to the trial interventions, the site will complete an SAE form and record the description, date of onset, end date, severity and assessment of relatedness to trial intervention.

For the purpose of safety recording for this trial, only unforeseeable SAEs potentially related to the intervention will be reported immediately to the central trial team. When the local research team becomes aware of an SAE in a trial participant, the PI will review the SAE locally and make a decision about the causality (i.e. likelihood of the event to be related/attributed to the intervention). Further details on the grades of causality are available in the SAE Reporting Guidelines document in the Investigator Site File. Following the assessment of causality the PI will assess any related events for expectedness. For any SAEs assessed as unexpected and potentially related, the details of the event will be entered on an SAE reporting form on the database, and the local research team will notify the central trial team via email or telephone within 24 hours of the PI becoming aware of the event. Once received, causality and expectedness will be confirmed by the Chief Investigator (CI) or delegate (Nominated Person). In the event that consensus is not reached between the PI and Nominated Person about assessment of causality and expectedness, this will be escalated to the CI for further discussion. However, if no consensus decision is reached about expectedness after further discussion within one working day, and the SAE is judged to be unexpected by any one of either the PI, Nominated Person or CI, the event will be classified as an unexpected event.

A serious adverse event (SAE) occurring to a participant should be reported to the REC that gave a favourable opinion of the study where in the opinion of the Chief Investigator the event was 'related' (resulted from administration of any of the research procedures) and 'unexpected' in

Clinical Research Protocol Template version 15.0

CONFIDENTIAL

© Copyright: The University of Oxford and Oxford University Hospitals NHS Foundation Trust 2019 Page 24 of 39

relation to those procedures. Reports of related and unexpected SAEs should be submitted within 15 working days of the Chief Investigator becoming aware of the event, using the HRA report of serious adverse event form (see HRA website). All such events will also be reported to the Trial Management Group (TMG) at their next meeting.

Adverse events (AEs) that are unrelated to the injury, intervention or treatment will not be reported.

# 10.3. Reporting Procedures for Foreseeable Serious Adverse Events and Adverse Events Not Defined as Serious

Foreseeable SAEs and adverse events not defined as serious that are related to the interventions will be recorded by participants (through a bespoke patient-reported complications questionnaire) or recruitment centre staff (on a site complication CRF) but will not need to be reported immediately.. These events will be verified with the participant and/or by the site investigators to ensure accurate recording and avoidance of duplicate reports over the follow-up timepoints.

Foreseeable adverse events include:

- pain increase after exercises that required an increase in analgesia or medical doctor consultation
- treatment-related exacerbations of other medical conditions after exercise that require medical treatment, which also do not meet the definition of serious (for example angina after exertion)
- Falls and injurious falls during performance of exercise that do not meet the definition of serious

Fracture management complications will be collected from participants in the 2, 4 and 6 month questionnaires but will not be reported as adverse events, these include:

- Deep Vein Thrombosis/Pulmonary Embolus
- Wound infection treated with antibiotics
- Heel or ankle pressure sore (grade II or above)
- Surgery/further surgery to the injured ankle (unless an adverse event directly related to the exercise intervention, in which case this would be an SAE)

# **11. STATISTICS AND ANALYSIS**

## 11.1. Statistical Analysis Plan (SAP)

Clinical Research Protocol Template version 15.0

CONFIDENTIAL

© Copyright: The University of Oxford and Oxford University Hospitals NHS Foundation Trust 2019 Page 25 of 39

The statistical aspects of the study are summarised here with full details of all analyses to be fully described in a separate statistical analysis plan. The SAP will be drafted early in the trial and finalised prior to the primary outcome analysis. The SAP will be reviewed by the TOC. Interim analyses of the efficacy outcomes are not planned and will be performed only if requested by the TOC. It is anticipated that all analysis will be undertaken using Stata (StataCorp LP, www.stata.com) or another well validated statistical package.

# 11.2. Sample Size Determination

292 (146 per arm) participants providing primary outcome data at 6 months are required to detect a difference of 8 points on the OMAS score with an estimated standard deviation of 21 with 90% power and 5% (2-sided) significance. The minimum clinically important difference for the OMAS selected in surgical trials has usually been 10 points but for this trial of physiotherapy we have chosen a smaller difference of 8 points, which is likely to be clinically important and was supported by our patient advisory group. The chosen standard deviation of 21 is based on the AIM trial (6) (SD 21.7) and the feasibility study data (SD 20.5 based on 32 participants having reached the 6 month time-point - unpublished). This equates to a standardised effect size of 0.38, a small to moderate effect. In the AFTER feasibility study there was 11% loss to follow-up (those not providing the primary outcome data). In order to allow for potential loss to follow-up of participants in the definitive trial we have inflated the sample size by 15% to 344 participants (172 per arm).

# 11.3. Analysis populations

11.4. Primary analysis population will be the intention-to-treat population (ITT), that is participants will be analysed in the group in which they were randomised regardless of what treatment they received. The analyses will be repeated for the per protocol population, which will be finalised using blinded data prior to the final datalock. Description of the Statistical Methods

All available data from both treatment arms will be used in data analysis based on the intentionto-treat population. Reporting of the results will be in accordance with the CONSORT statement (34) using the extensions for non-pharmacological treatment interventions and patient-reported outcomes. Standard descriptive statistics will be used to describe the demographics between the treatment groups reporting means and standard deviations or medians and interquartile ranges as appropriate for continuous variables and numbers and percentages for binary and categorical variables. Standard statistical summaries and graphical plots will be presented for the primary outcome measure and all secondary outcome measures.

The OMAS score at 6 months is the primary outcome in this study and will be compared between treatment groups as the dependent variable in a mixed-effects linear regression model including outcome information at intermediate time-points. This model will adjust for stratification factors

Clinical Research Protocol Template version 15.0

CONFIDENTIAL

© Copyright: The University of Oxford and Oxford University Hospitals NHS Foundation Trust 2019 Page 26 of 39

(recruitment centre and initial fracture management; operative or non-operative) and baseline OMAS score. A random effect will be included to account for heterogeneity due to recruitment centres. The treatment effect will be based on adjusted mean differences at 6 months and will be reported together with their 95% confidence intervals.

We will also undertake a Complier Average Causal Effect (CACE) analysis which essentially compares the "compliers" in each group. Full compliance in the intervention group is defined as receiving a minimum of 4 physiotherapy sessions and partial compliance is receiving at least one physiotherapy session (i.e. starting the treatment). This will provide supporting evidence to any findings from the principal analysis. Subgroup analysis by surgical vs non-surgical treatment of the fracture, and by self-perceived self-efficacy at baseline will be undertaken using the same methodology incorporating a treatment by subgroup interaction term and presented using forest plots.

Similar methods to the primary outcome will be used to analyse continuous secondary clinical outcomes and patient reported outcomes. Complications will be reported by type for each intervention group, and, if appropriate, compared between the two groups using logistic regression models.

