A James Lind Priority Setting Partnership on lower limb fragility fractures ranked 'What is the best physiotherapy and/or occupational therapy regime for adults during out-of-hospital recovery from a fragility fracture of the lower limb?' as second in the top ten, highlighting the importance of this research to clinicians, patients and carers.(12) Ankle fractures have a substantial impact on people's lives, resulting in mobility problems and reduced independence, and prognosis worsens with increasing age.(13) It is uncertain why people fare worse as they age but lower physiological reserves, comorbidities, reduced muscle mass and power (sarcopenia), and balance impairments are likely to contribute.(14) The resultant disability after injury has a significant associated socioeconomic burden, impacting on an individual's capacity to work, care for others, and perform daily activities.(5)

Clinical Research Protocol Template version 15.0

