### 8.2. Inclusion Criteria

- Patient is aged 50 years and over with an ankle fracture undergoing surgical fixation or non-surgical management
- Patient has been provided with a cast or orthotic boot (non-removable or removable for non-weight bearing ankle movement) for at least 4 weeks and no longer than 10 weeks.
- Patient has capacity to consent to trial participation within 14 days of removal of the cast/boot.

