## 9.7. Baseline Assessments

Baseline sociodemographic, injury, mobility, height, weight, smoking status, diabetes diagnosis and alcohol consumption data will be collected in the baseline CRF. Participants will also be asked to complete the validated questionnaires outlined in section 6.

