## 11.6. **Procedure for Accounting for Missing, Unused, and Spurious Data.**

Missing data will be minimised by careful data management. Missing data will be described with reasons given where available; the number and percentage of individuals in the missing category will be presented by treatment arm. All data collected on data collection forms will be used, since only essential data items will be collected. No data will be considered spurious in the analysis since all data will be checked and cleaned before analysis. The nature and mechanism for missing variables and outcomes will be investigated, and if appropriate multiple imputation will be used. However, the analysis method proposed is reasonably robust to missing at random (MAR) data. Sensitivity analyses will be undertaken to assess potential departures from the missing at random assumption. Any imputation techniques will be fully described in the Statistical Analysis Plan.

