### CONFIDENTIAL

© Copyright: The University of Oxford and Oxford University Hospitals NHS Foundation Trust 2019 Page 28 of 39

participants/recruitment centre and server. All electronic patient-identifiable information will be held on a server located in an access-controlled server room at the University of Oxford. The data will be entered into a Good Clinical Practice (GCP) compliant data collection system and stored in a database on the secure server, accessible only to the research team based on their role within the study. The database and server are backed up to a secure location on a regular basis.

Identifiable data will be limited to contact details (including name, address including postcode, and email addresses), NHS/ CHI number, sex at birth, DOB and telephone numbers and will be accessed separately from the outcome data obtained from/about the participants and managed within the rules of the clinical database system. In all other data, participants will be identified by a trial ID only. Direct access to source data/documents will be required for trial-related monitoring and/or audit by the Sponsor, NHS Trust or regulatory authorities as required. Contact details will be retained for 12 months after the last data collection. Electronic de-identified trial data will be retained for three years after publication of the trial.

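### Adding age, which the protocol calls prognostic and already holds, to the primary OMAS model would be a free but modest improvement

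*Protocol*

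**What the plan says.** Section 11.4, Description of the Statistical Methods (its heading runs into the text of 11.3), specifies a "mixed-effects linear regression model including outcome information at intermediate time-points". The adjustment set is named in closed form: "recruitment centre and initial fracture management; operative or non-operative) and baseline OMAS score", with a random effect for centre. The same section carries similar methods over to the continuous secondary outcomes. Section 9.4 minimises on centre and initial fracture management only.

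On age, the background (section 5) says that "prognosis worsens with increasing age". Eligibility sets a floor but no ceiling: "Patient is aged 50 years and over with an ankle fracture" (section 8.2). Age can be derived for everyone, because section 12 lists "NHS/ CHI number, sex at birth, DOB and telephone numbers" among the data held, and the screening log in section 9.2 also records age.

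On missing data, section 11.6 says that "the analysis method proposed is reasonably robust to missing at random (MAR) data". It also plans to investigate the missingness mechanism, to use multiple imputation if appropriate, and to run sensitivity analyses for departures from missing at random. Section 11.1 leaves full analysis detail to a separate SAP.

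**The concern.** The protocol names a variable as prognostic, holds it for every participant, and then leaves it out of a covariate list that it writes out. No reason is given. In a linear model, whatever age explains beyond the listed covariates stays in the residual variance and widens the confidence interval for the treatment difference. Since age is not minimised on either, a chance difference in age between the arms moves the observed estimate. A prespecified adjustment removes that shift, whereas adding age after an imbalance has been seen is open to challenge.

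There is also a link to missing data. A likelihood-based mixed model relies on missingness being at random given what is in the model. If older participants respond less often, a model without age has less support for that assumption.

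What is at stake is some precision, and some robustness of the primary estimate to chance imbalance. The validity of the trial is not in question.

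**Working it through.** **1. The plan's own figure.** Inputs from section 11.2: difference 8, SD 21, two-sided 5%, power 90%, 15% loss.

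- Normal approximation: n per arm = 2 × (21 × (1.960 + 1.282) / 8)² = 144.8, so 145 per arm (290).
- Noncentral t: 145 per arm gives 89.85% and 146 gives 90.04%, so 146 per arm (292).
- Loss: 292 / 0.85 = 343.5, so 344.

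The stated 292 and 344 reproduce. They use the SD of 21 with no credit for any covariate, so leaving age out takes nothing away from the planned power.

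**2. Precision with age added.** Let r be the partial correlation of age with 6-month OMAS given the other covariates. The protocol gives no value, so r is assumed over a range. Residual SD = 21 × √(1 − r²); SE = SD × √(2/146); power by normal approximation = Φ(8/SE − 1.96); effective N = 292 / (1 − r²).

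| r | variance explained | SD | 95% CI half-width | power | effective N |
|---|---|---|---|---|---|
| 0 | 0% | 21.00 | 4.82 | 90.2% | 292 |
| 0.1 | 1% | 20.89 | 4.79 | 90.5% | 295 |
| 0.2 | 4% | 20.58 | 4.72 | 91.3% | 304 |
| 0.3 | 9% | 20.03 | 4.60 | 92.7% | 321 |
| 0.316 | 10% | 19.92 | 4.57 | 92.9% | 324 |

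**3. Allowing for baseline OMAS.** The table applies r to the unadjusted SD, although r is defined as what age adds to the other covariates. If baseline OMAS already explains variance, the starting SD is lower and less power is left to gain. With an assumed baseline correlation of 0.5, the starting SD is 21 × √(1 − 0.25) = 18.19 and power is 96.4%. Adding age with r from 0.1 to 0.3 gives SDs of 18.10 to 17.35 and power of 96.5% to 97.6%.

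**4. Chance imbalance.** With 146 per arm, the standardised age difference between arms has standard error √(2/146) = 0.117. The resulting shift in the OMAS difference has a 95% range of ±1.96 × 0.117 × 21 × r. That is about ±0.5 points at r = 0.1, ±1.0 at 0.2 and ±1.4 at 0.3, against a target of 8.

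**5. Missing data.** This was a large-sample simulation with OMAS depending on arm and age only, 15% missing at the mean age, and log-odds of missing changing by 0.8 per SD of age. All of these are assumptions. Bias in the treatment difference without age in the model was as follows:

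- Age drives missingness equally in both arms: about 0 (under 0.05 points, simulation noise).
- In one arm only: about 0.3, 0.5 and 0.75 points for r = 0.1, 0.2 and 0.3.
- In opposite directions in the two arms, an extreme case: about 0.5, 1.1 and 1.7 points.

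Adding age brought the bias to within simulation noise of zero in each case. The simulation omits baseline, 2-month and 4-month OMAS, which would carry part of the same information.

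**The case against.** The strongest reply is that nothing is wrong. Adjusting for the minimisation factors and the baseline outcome is a standard, valid intention-to-treat analysis, and the SAP may still add age. The sentence on prognosis is background. It is not confined to people over 50 or to 6-month OMAS, and cutting the population off at 50 probably weakens the association. The gain is assumed and small. Chance imbalance in age is random error that the confidence interval already covers, as it does for smoking, diabetes or weight, all of which section 9.7 collects. All of this stands, and it limits the point to an improvement. It does not remove the point: the covariate list is written out in the protocol, age is the factor that the protocol singles out as prognostic, and adding it does no harm.

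Three stronger readings are tempting but not supported:

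- A reader might infer that the trial is short of power. It is not, because the sample size takes no credit for covariates.
- A reader might infer that the missing-at-random claim in section 11.6 fails, or that the treatment estimate is biased. That needs age to predict non-response, and to do so differently by arm (or age to modify the treatment effect). The protocol states neither. The intermediate scores, possible imputation and planned sensitivity analyses reduce the concern further, although intermediate scores do not help for participants who return no follow-up at all.
- A reader might infer that baseline OMAS, taken around removal of the cast or boot, cannot reflect age. The protocol gives neither its distribution nor its relation to age.

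**Conclusion.** The point holds as a free, modest improvement. The primary model omits a covariate that the protocol calls prognostic and already holds. For an assumed 1% to 10% of residual variance explained, the power gain is about 0.3 to 2.7 percentage points (90.2% to between 90.5% and 92.9%) with the SD at 21. It is smaller if baseline OMAS is already predictive: about 0.1 to 1.2 points at an assumed baseline correlation of 0.5. The 95% CI half-width falls by at most about a quarter of a point (4.82 to 4.57). Protection against chance age imbalance is of the order of 0.5 to 1.5 OMAS points at the 95% limits, under the same assumptions. The benefit for missing-data bias is conditional on an arm-dependent relation between age and response, and should not be claimed as established.

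**What to change.** In section 11.4, and correspondingly in the SAP, add age at randomisation as a continuous, linear, prespecified fixed covariate in the primary OMAS model and in the continuous secondary outcome models that use the same method. Include age in any imputation model under section 11.6. Make the change before any unblinded outcome data are seen, and leave the minimisation in section 9.4 as it is. If the sponsor prefers to leave age out, one sentence giving the reason would settle the point.

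The cost is one phrase in the text and one degree of freedom in each model. No new data are needed, because age follows from date of birth and the randomisation date.

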## Intervention quality assurance and fidelity:

All clinical staff delivering the interventions will be trained to enhance standardisation of the study procedures. Sites will identify physiotherapists that will deliver the AFTER supervised rehabilitation intervention and receive the training. We will ask that the AFTER trained physiotherapists are not involved in the rehabilitation of participants in the self-management group as far as it is practical to do so. Also, physiotherapists not trained in the AFTER supervised rehabilitation will be asked not to deliver the intervention. Although this has been feasible in other rehabilitation trials to limit potential contamination, we appreciate this can be challenging so we will ask staff to record where this occurs so issues can be identified and addressed during the trial.

Clinical Research Protocol Template version 15.0

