### CONFIDENTIAL

© Copyright: The University of Oxford and Oxford University Hospitals NHS Foundation Trust 2019 Page 21 of 39

A rigorous process of fidelity checks will be conducted to ensure fidelity of intervention delivery.(33) Treatment case report forms will be used to monitor intervention fidelity. Data will be collected with regards the health professional delivering the intervention (profession, grade), the intervention content delivery and the number of treatment sessions attended, to facilitate monitoring and reporting. If deemed necessary, site visits and/or audio/video recording of interventions will be conducted. Permission will be sought, and verbal consent recorded, from the trial participants to observe or record treatment sessions. The sites will regularly receive feedback from quality assurance activities to help maintain and improve fidelity.

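### Therapist clustering in the supervised arm is allowed for in neither the primary model nor the 90% power, and no therapist identifier is among the data listed for collection

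*Protocol*

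**What the plan says.** Section 11.4 compares OMAS at 6 months in a "mixed-effects linear regression model including outcome information at intermediate time-points", adjusted for baseline OMAS, initial fracture management and centre. It adds: "A random effect will be included to account for heterogeneity due to recruitment centres". No term for the treating physiotherapist appears.

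Section 11.2 sets the sample size to detect 8 points with SD 21, "with 90% power and 5% (2-sided) significance". No design effect is mentioned.

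Section 9.6 describes the supervised arm as 4 to 6 one-to-one physiotherapy sessions. It states that "Sites will identify physiotherapists that will deliver the AFTER supervised rehabilitation intervention" and are trained for it. Those therapists are asked not to treat self-directed participants where practical, and untrained physiotherapists are asked not to deliver the programme.

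On data capture, section 9.6 says "Data will be collected with regards the health professional delivering the intervention (profession, grade"; the bracket closes there, and the list goes on to content delivered and sessions attended. Section 9.8 lists the clinician's profession and experience for the treatment logs. Neither list includes a code that identifies the therapist.

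**The concern.** Participants treated by the same physiotherapist share that person's skill and style. Here the sharing arises in one arm: the supervised participants are nested within therapists, while the self-directed participants mainly receive standardised advice materials. This is a partially nested design.

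A random centre intercept shifts both arms of a centre together and so cancels from the within-centre treatment comparison. A therapist effect that exists only in the supervised arm does not cancel. With one therapist per centre it acts exactly like a treatment-by-centre effect. If it is left out, the standard error of the treatment effect is understated and the real power falls below the stated figure.

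Both errors matter here. Understated standard errors favour a false claim of superiority, and section 5 says that a failure to show superiority would support disinvestment from routine physiotherapy. The statistical analysis plan can add a model term later, but not a grouping variable that was never recorded, and the power behind 344 is fixed in the protocol.

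**Working it through.** **Inputs from the protocol.** Difference 8, SD 21, two-sided 5%, 90% power, 146 per arm analysed, 15% loss (section 11.2); at least 20 hospitals (section 7).

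**Assumptions, not in the protocol.** Exactly 20 sites, one or two therapists per site, therapist ICC 0.02 to 0.05.

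**Step 1: reproduce the plan.** n per arm = 2 × (21 × (1.960 + 1.282)/8)² = 144.8. The t-test version gives 145.8, so 146 per arm and 292 in all. Then 292/0.85 = 343.5, so 344. With 146 per arm, SE = 21 × √(2/146) = 2.458 and power = Φ(8/2.458 − 1.960) = 90.2%. The stated figures are reproduced with no clustering term.

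**Step 2: add clustering in one arm.** Supervised participants per therapist: m = 146/20 = 7.3 (one per site) or 146/40 = 3.65 (two per site). Design effect in that arm: DE = 1 + (m − 1) × ICC. True SE = 21 × √(DE/146 + 1/146), which is 2.458 × √((DE + 1)/2).

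**Step 3: consequences.** Power = Φ(8/SE − 1.960). Type I error if the model's SE stays at the unclustered value = 2 × (1 − Φ(1.960 × 2.458/SE)). Analysed n per arm for 90% power = (21 × 3.242/8)² × (1 + DE), then divide the total by 0.85.

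| Therapists per site | ICC | DE | SE | SE increase | Power | Type I error if ignored | Randomised N for 90% |
|---|---|---|---|---|---|---|---|
| 1 | 0.02 | 1.126 | 2.534 | 3.1% | 88.4% | 5.7% | 363 |
| 1 | 0.05 | 1.315 | 2.645 | 7.6% | 85.7% | 6.9% | 396 |
| 2 | 0.02 | 1.053 | 2.490 | 1.3% | 89.5% | 5.3% | 351 |
| 2 | 0.05 | 1.133 | 2.538 | 3.3% | 88.3% | 5.8% | 365 |

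The last two rows also describe 40 sites with one therapist each.

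**Step 4: what baseline adjustment could recover.** Section 11.2 takes no credit for adjusting for baseline OMAS. Let r be its correlation with the 6-month score (also not given), and let adjustment reduce only patient-level variance. With one therapist per site, the planned power is restored when m × ICC + (1 − ICC)(1 − r²) + (1 − r²) = 2.

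- ICC 0.02: 0.146 + 1.98(1 − r²) = 2, so r is about 0.25.
- ICC 0.05: 0.365 + 1.95(1 − r²) = 2, so r is about 0.40.

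Adjustment does not remove the therapist component. At ICC 0.05 and r = 0.40, its share of the remaining variance rises from 0.05 to 0.05/(0.05 + 0.95 × 0.84) = 0.059.

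**The case against.** The strongest reply is that the effect is small and rests on assumed inputs. The protocol gives no ICC and no number of therapists, and 20 hospitals is a minimum, so one therapist at each of exactly 20 sites is the most clustered of the cases shown. The programme is structured, with a manual, training and fidelity checks, all of which argue for a low ICC. This stands: the figures are a range under assumptions, not a measured inflation.

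Baseline adjustment could also plausibly restore the power. That stands for power but not for the understated standard error.

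Next, section 11.1 leaves "full details of all analyses to be fully described in a separate statistical analysis plan", so a therapist term could appear there, and the data lists do not claim to be exhaustive. This stands in part. Sites know whom they trained, so a link might be rebuilt, but the lists as written give no assurance of it, and the power statement belongs to the protocol.

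A reader might infer something stronger: that because centre is the only random effect named, a participant's repeated OMAS scores are treated as independent, and the claim in section 11.6 that "the analysis method proposed is reasonably robust to missing at random (MAR) data" therefore fails. The protocol does not support this. It nowhere says that centre is the sole random effect or that scores within a participant are independent. A mixed model that uses the intermediate scores ordinarily models their correlation, and its covariance structure is detail for the statistical analysis plan. Material bias at 6 months would need both an independence model and dropout strongly tied to earlier scores in different ways by arm; the text states neither. Section 11.6 also plans sensitivity analyses for departures from missing at random.

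**Conclusion.** The point holds for therapist clustering only. The protocol describes a partially nested design, names a centre effect that cannot account for it, states a power that assumes it away, and lists no identifier with which to model it. For ICC 0.02 to 0.05 with one or two therapists at each of 20 sites, the standard error is understated by about 1% to 8% of its nominal value. Power before covariate gain is about 86% to 89.5% instead of 90%, and type I error if clustering is ignored is about 5.3% to 6.9% instead of 5%. More sites or more therapists per site would shrink all of these. This is a modest weakness that is worth correcting because the correction is cheap and the grouping variable is best captured prospectively. It does not invalidate the trial and does not touch the handling of repeated scores or missing data.

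**What to change.** - **Data capture (sections 9.6 and 9.8).** Add an anonymised therapist code to the treatment log for each supervised session.
- **Analysis (section 11.4).** State that therapist clustering in the supervised arm will be accounted for with a partially nested random effect, at least as a prespecified sensitivity analysis of the primary outcome. If codes are incomplete, use a random treatment-by-centre effect instead.
- **Sample size (section 11.2).** State that the 90% power assumes no therapist clustering, and give the power for ICC 0.02 to 0.05 under stated numbers of therapists per site.

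The cost is one log field and a few sentences, a slightly wider confidence interval where the clustering is modelled, and a slightly less favourable stated power.
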